2.2. Secondary Objectives

- To evaluate the continued efficacy of Cannabidiol Oral Solution after the 14-day treatment with vigabatrin or vigabatrin plus Cannabidiol Oral Solution is complete.
- To evaluate the safety and tolerability of Cannabidiol Oral Solution as adjunctive therapy with vigabatrin as initial therapy in treating patients with Infantile Spasms.

3. INVESTIGATIONAL PLAN

3.1. Overall Study Design

This is a Phase 3, double-blind, placebo-controlled, randomized, multicenter study to evaluate the efficacy, safety, and tolerability of Cannabidiol Oral Solution (CBD) as adjunctive therapy with vigabatrin as initial therapy, compared to vigabatrin alone in the treatment of infants newly diagnosed with Infantile Spasms (IS). Randomization will occur during Visit 2 and then allocated to one of two treatment groups:

- Treatment with vigabatrin plus
- CBD 40 mg/kg/day, or
- Matching CBD 40 mg/kg/day placebo

Approximately, 190 patients in total will be enrolled into one of the two treatment arms; 130 patients in the investigational product arm with 60 patients in the placebo arm. Patients will be dosed approximately every 12 hours with meals to help ensure consistent plasma levels are achieved and to reduce variability.

Doses of CBD exceeding 40 mg/kg/day will not be examined in this study. In addition to the safety assessments required by the study protocol, the investigator will monitor patients throughout the study as recommended in the approved product label for vigabatrin. Study participants will be newly diagnosed pediatric patients age 1 to 24 months (inclusive) experiencing infantile spasms who satisfy all inclusion/exclusion criteria. This study will be comprised of five periods: Screening, Initial Treatment, Extended Treatment, Taper, and Follow-up Periods, with a maximum duration of approximately 140 days.

The study design and patient progression through the study is outlined in [Figure 1](#). All screening, efficacy, and safety evaluations will be performed according to the schedule of assessments summarized in [Table 1](#).

Each newly diagnosed patient with Infantile Spasms will complete a Screening Period and will have up to 14 days to enroll in the study.

Patients will have a, minimum of a 9-hour video EEG that includes at least one full sleep-wake cycle during their Screening Visit to establish their baseline level of infantile spasms and hypsarrythmia and a 24-hour video EEG at Visit 5 (Day 14 to Day 15) of the Initial Treatment Period to establish their final level of infantile spasms and hypsarrythmia. A blinded central reader, not involved in the study, will evaluate the video EEGs and determine responder status. Details of the video EEG assessment will be provided in the video-EEG Charter. The treatment response categories are summarized in [Table 2](#). In addition, a 9-hour video EEG will be conducted during the Extended Treatment Period to confirm parent/caregiver report of relapse. If possible, a 9-hour video EEG will be conducted for patients who have continued into the Extended Treatment Period and decided to Early Withdraw. A video EEG is not required for patients who decide to withdraw during the Initial Treatment Period.

Table 2: Video EEG Response Definitions

Response Category	Definition
Complete Response	Complete resolution of spasms and hypsarrythmia confirmed by video EEG
Partial Response	Complete resolution of either spasms or hypsarrythmia confirmed by video EEG
Non-Response	No improvement or worsening of spasms/hypsarrythmia burden

3.1.1. Initial Treatment Period

- Day 1 (Visit 2): Patients will receive the initial titration dose of vigabatrin (50 mg/kg/day divided twice daily [BID]), and either CBD 20 mg/kg/day plus matching CBD 20 mg/kg/day placebo or CBD 40 mg/kg/day placebo, each drug administered BID for 3 days.
- Day 4 (Visit 3): Patients will return to the study center to evaluate medical status (seizure diary, vital signs, and neurological exam), clinical laboratory assessments, concomitant medications, height/weight, and assess adverse events (AEs). For those patients who tolerate the initial dose, the dose for vigabatrin will be increased to 100 mg/kg/day BID, and either CBD 30 mg/kg/day and matching CBD placebo 10 mg/kg/day, or matching CBD 40 mg/kg/day BID placebo for 3 days.
- Day 7 (Visit 4): Patients will return to the study center to evaluate medical status (seizure diary, vital signs, and neurological exam), clinical laboratory assessments, concomitant medications, height/weight, and assess AEs. For those patients who tolerate the increased doses, the dose of vigabatrin will be increased to 150 mg/kg/day and CBD or CBD placebo to 40 mg/kg/day for the remaining 9 days. Vigabatrin, CBD, and matching placebo will be administered in a twice daily fashion at 12-hour intervals with meals.

As part of their standard of care, investigators will assess safety and tolerability of the treatment regimens throughout the study period. All subjects will continue on their treatment until confirmation from the central reader on the 24-hour video EEG and clinical laboratory results are received.

3.1.2. Extended Treatment Period

Following the Initial Treatment Period:

- Complete Responders will continue receiving their assigned treatments of vigabatrin plus either CBD 40 mg/kg/day or placebo for 75 days, until Week 13 (Day 90), to monitor progress for treatment response.
- During the Extended Treatment Period, the investigator may reduce the dose of CBD or CBD placebo to 30 mg/kg/day for safety or tolerability. If the subjects cannot tolerate the 30 mg/kg/day, the drug will be discontinued and the patient withdrawn from the study following the completion of the taper period.

3.1.3. Partial Responders

- Partial responders will be offered the opportunity to enroll in an open-label safety study that allows investigators to combine standard-of-care treatment with CBD.

3.1.4. Taper Period

Following the completion of the Initial Treatment Period (Visit 6), partial responders who do not enroll in the open-label safety study and non-responders will have vigabatrin and CBD tapered as follows:

- Vigabatrin taper: 150 mg/kg/day will be reduced to 100 mg/kg/day for 3 days, then the 100 mg/kg/day dose will be reduced to 50 mg/kg/day for 3 days, and then discontinued.
- CBD or CBD Placebo taper: 40 mg/kg/day will be reduced to 30 mg/kg/day for three days, then 30 mg/kg/day will be reduced to 20 mg/kg/day for 3 days, and then discontinued.

Complete Responders will be tapered off vigabatrin and CBD or CBD placebo at the completion of the Extended Treatment Period, and all patients will be tapered off at any Early Withdrawal Visits, using the same schedules as described above.

[figure not shown]
If the investigator decides to continue vigabatrin as a treatment for patients after the end of study or early withdrawal, tapering of vigabatrin will be left to the discretion of the PI.

CBD requires tapering off at the End of Study or at the Early Withdrawal visit.

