^e Vital signs will be taken after approximately 5 minutes seated or supine, depending on patient ability. On Day 1 (Visit 2), vital signs should be taken predose and at 4 hours postdose. On all other days, the assessment will be completed predose.

^f A brief neurological examination will be performed, except for the Screening Visit, Visit 6, Visit 9 and Early Withdrawal which will be a complete neurological exam. On Day 4 (Visit 3), and Day 7 (Visit 4) a brief neurological examination will be performed predose and approximately 2 hours following administration of the morning dose of the investigational product. Additional examinations may be performed at the discretion of the investigator.

^g On Day 1 (Visit 2), patients will receive the initial titration dose of vigabatrin (50 mg/kg/day divided twice daily [BID]), and either CBD 20 mg/kg/day plus matching CBD 20 mg/kg/day placebo or CBD 40 mg/kg/day placebo, each drug administered twice daily for three days.

^h For those patients who tolerate the initial dose, the dose for vigabatrin will be increased to 100 mg/kg/day [BID], and either CBD 30 mg/kg/day plus matching CBD 10 mg/kg/day, or CBD 40 mg/kg/day placebo for 3 days. On Day 7 (Visit 4) the dose of vigabatrin will be increased to 150 mg/kg/day and CBD to 40 mg/kg/day for the remaining 9 days for subjects who tolerate the previous dose.

ⁱ Complete Responders will continue receiving their assigned treatments of vigabatrin plus either CBD 40 mg/kg/day or matching placebo for 75 days, until Week 13 (Day 90) to monitor treatment response. During the extended treatment period the Investigator can only down titrate once to 30 mg/kg/day.

^j All subjects will be tapered off vigabatrin as follows: 150 mg/kg/day will be reduced to 100 mg/kg/day for 3 days then the 100 mg/kg/day will be reduced to 50 mg/kg/day for 3 days and then discontinued. Similarly, all subjects will be tapered off CBD or CBD Placebo according to the following schedule: 40 mg/kg/day will be reduced to 30 mg/kg/day for 3 days, then 30 mg/kg/day will be reduced to 20 mg/kg/day for 3 days, then discontinued. Patients will receive a follow-up phone call 4 weeks after completing the tapering. Drug reconciliation will be completed at the end of study.

^k A blood sample for PK analysis will be obtained on Day 15 prior to the second dose during the 24-hour video EEG.

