3.4. Dose Adjustment Criteria

During the Extended Treatment Period, the investigator may reduce the dose of CBD or CBD placebo once from 40 mg/kg/day to 30 mg/kg/day for safety or tolerability. In addition, tapering of vigabatrin and CBD will be required as described in [Section 3.1.4](#).

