7.2.5. Early Withdrawal Visit

Should a patient's participation be terminated prior to Day 14 or Day 90 for any reason (see [Section 3.3](#)), an Early Withdrawal Visit will be completed. The following procedures will be completed:

- Record concomitant medications and AETs.
- Record vital signs (seated or supine blood pressure ([depending on patient age and ability]), pulse rate, respiratory rate, and temperature measurements).
- Record height and weight and head circumference.
- Record and review daily seizure diary.
- Perform a complete neurological examination (see [Section 6.2.3](#)).
- Complete investigator CGI-I.
- Record AEs.
- Perform 9-hour video EEG, if possible only for patients that continued into the Extended Treatment Period.
- Draw blood samples for hematology and chemistry.
 - [Section 7.4](#) details the volume of samples to be drawn based on patient age.

All patients will begin tapering off investigational product and vigabatrin at this visit (see [Section 7.2.2](#)).

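### Section 3.5 discontinues infants at hepatic thresholds without saying how CBD is stopped, while the taper text requires a CBD taper at every early withdrawal (up to 150 mg/kg over 6 days from full dose)

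*Protocol*

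**What the plan says.** Protocol Section 3.5 (Stopping Rules) discontinues a patient at any of four liver findings:

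- ALT or AST above 8 × ULN
- ALT or AST above 5 × ULN lasting more than two weeks
- ALT or AST above 3 × ULN with bilirubin above 2 × ULN or INR above 1.5
- ALT or AST above 3 × ULN with listed symptoms or eosinophilia

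It does not say how CBD is to be stopped.

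The taper text does say how. In Section 3.1.4, "all patients will be tapered off at any Early Withdrawal Visits, using the same schedules as described above", and the first CBD step is that "40 mg/kg/day will be reduced to 30 mg/kg/day for three days", followed by 20 mg/kg/day for three more days. The same section adds that "CBD requires tapering off at the End of Study or at the Early Withdrawal visit". Sections 4.1.4 and 7.2.2 and the synopsis repeat this. Section 3.4 says that "tapering of vigabatrin and CBD will be required as described in" Section 3.1.4. Table 1 footnote j says that "all subjects will be tapered off CBD or CBD Placebo according to the following schedule".

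Section 7.2.5 applies the Early Withdrawal Visit when "participation be terminated prior to Day 14 or Day 90 for any reason", and there: "All patients will begin tapering off investigational product and vigabatrin at this visit". The only discretion over tapering concerns vigabatrin that the investigator chooses to continue as treatment. The blood draw at that visit is listed as "Draw blood samples for hematology and chemistry". No laboratory test is scheduled in the Taper Period.

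**The concern.** A liver stopping rule exists to end exposure to a drug that may be causing injury. Here the only instructions on how CBD ends tell the site to keep giving it, at reduced dose, to every infant who leaves early. A site that follows the taper text continues CBD for up to six days after a liver signal. A site that reads Section 3.5 as an immediate stop gives none. Two infants who meet the same rule can therefore be treated differently, with neither site clearly wrong.

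It matters most for transaminases above 8 × ULN, and for values above 3 × ULN with raised bilirubin, raised INR or symptoms. It matters less for the rule of more than 5 × ULN for over two weeks, because that rule already accepts two weeks of dosing. The issue is patient safety only. Power, the primary comparison and the secondary analyses are not touched.

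**Working it through.** **Inputs**

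- Taper steps from 40 mg/kg/day: 30 mg/kg/day for 3 days, then 20 mg/kg/day for 3 days, then stop (Section 3.1.4).
- Length of the Taper Period: 6 days (Table 1).
- Full dose 40 mg/kg/day, reached on Day 7. Starting dose 20 mg/kg/day (Section 3.1.1).

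**The plan's own figure.** 3 + 3 = 6 days, which agrees with Table 1. The documents state no cumulative taper dose.

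**Extra CBD after a hepatic stop, literal reading, infant on 40 mg/kg/day**

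- First step: 30 × 3 = 90 mg/kg
- Second step: 20 × 3 = 60 mg/kg
- Total: 90 + 60 = 150 mg/kg over 6 days
- Mean: 150 / 6 = 25 mg/kg/day, which is 25 / 40 = 62.5% of full dose and above the starting dose
- Equivalent to 150 / 40 = 3.75 days at full dose

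On the immediate-stop reading, the total is 0 mg/kg.

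**Lower doses.** The protocol gives no separate taper for an infant on less than 40 mg/kg/day. Assuming that an infant on 30 mg/kg/day takes only the last step, the total is 20 × 3 = 60 mg/kg over 3 days. There is no written step below 20 mg/kg/day. A placebo infant receives no CBD on any reading.

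**The texts side by side**

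1. Section 3.5 requires discontinuation and is silent on the taper.
2. Section 7.2.5 covers termination for whatever reason and starts the taper for everyone at that visit. A hepatic stop is not carved out.
3. Table 1 footnote m sends patients who stop drug early to the Early Withdrawal Visit. This leaves room for a stop before the visit, but it is also the visit at which Section 7.2.5 starts the taper.
4. Section 3.1.2 withdraws a patient who cannot tolerate 30 mg/kg/day only after the taper is complete. So at least one exit for tolerability passes through the taper.
5. Section 9.8 allows departure from the protocol to remove an immediate hazard. It is a general clause that requires the departure to be recorded and reported, not a rule for hepatic stops.

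The SAP does not settle the matter. Its Section 4.4 also tapers everyone at early withdrawal. Its 3-day taper (Section 4 and Table 2) belongs to protocol V2.0 of 30 October 2017, whose dosing differs, so the 6-day protocol schedule is used here.

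**The case against.** The best reply is that Section 3.5 already means an immediate stop. It sits under a heading about stopping, and it is specific where the taper text is general. Where the protocol wants a taper before a tolerability exit, Section 3.1.2 says so, and Section 3.5 has no such words. Section 3.3 lets the investigator end treatment in the patient's interest. Section 6.2.6.5 lists drug discontinuation separately from dose modification. If danger is acute, Section 9.8 permits a departure. This much stands: the immediate-stop reading is reasonable. It does not remove the conflict, because Section 7.2.5 covers every reason for termination and every patient, and foreseeable care under a pre-specified liver rule should not depend on a protocol deviation.

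A second reply is that the speed of withdrawing an anti-seizure drug from an infant with spasms is a two-sided clinical choice. That also stands, and it is why the fix leaves room for a documented exception.

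A reader might infer three stronger things that the documents do not support:

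- *That the protocol certainly commits such infants to 150 mg/kg more CBD.* It does so only on the literal reading, and only from 40 mg/kg/day in the CBD arm.
- *That these infants go unmonitored during the taper.* Chemistry is drawn at the Early Withdrawal Visit. Section 6.2.6.1 counts an abnormal laboratory value as a possible adverse event and lets the investigator order further tests. Sections 3.3, 6.2.6.8 and 7.2.7 require follow-up. An extra mandatory liver panel would add little.
- *That many infants would be harmed.* No hepatic-stop rate is given, and nothing in the documents measures harm from six days of declining dose.

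**Conclusion.** The point holds as a conflict in the text. Section 3.5 orders discontinuation for liver findings without saying how, and every section that does say how requires a CBD taper with no hepatic exception. On the literal reading, the consequence is up to 150 mg/kg of CBD over 6 days for an infant on 40 mg/kg/day. On the other reading it is none. The figure of about 60 mg/kg from 30 mg/kg/day rests on the assumption that only the 20 mg/kg/day step applies. How many infants would be affected is unknown and probably small.

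This is a cheap improvement on patient-safety grounds, held with moderate confidence because Section 3.5 can fairly be read either way.

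**What to change.** Add to Section 3.5: when a hepatic rule in this section is met, CBD or placebo is stopped without the Section 3.1.4 taper by default, identically in both arms, unless the investigator documents a seizure-risk reason for a shortened taper. Cross-refer to it from Sections 3.1.4, 3.4, 4.1.4, 7.2.2 and 7.2.5, Table 1 footnote j and the synopsis. The taper for all other patients stays as it is.

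A stated default is better than open discretion, which would write the between-site difference into the protocol. No extra liver panel is needed.

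The cost is one short rule and its cross-references in a single amendment. No patients or blood samples are added and no analysis changes. The blind is kept because the rule is the same for CBD and placebo. The downside is abrupt CBD withdrawal in a few infants, which the documented exception is meant to limit.

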3.1.5. Follow-up Period

A follow-up phone call will occur for all subjects 30 days after discontinuation of the study drug to assess AEs, AETs, and record concomitant medications.

Figure 1: Study Design Schematic

3.2. Patient Selection

Each patient must satisfy all of the following inclusion and exclusion criteria.

3.2.1. Inclusion Criteria

All patients must satisfy the following criteria to be considered for study participation:

1. Parent(s)/caregiver(s) fully comprehend and sign the informed consent form, understand all study procedures, and can communicate satisfactorily with the investigator and study coordinator, in accordance with applicable laws, regulations, and local requirements.
2. Male or female between 1 months to 24 months of age (inclusive) at time of consent.
3. Clinical diagnosis of infantile spasms, confirmed by video-EEG analysis (including at least one cluster of electroclinical spasms [≥ 3 in any 10-minute epoch]) and hypsarrhythmia) obtained during the Screening Period and read by a central reader.
4. General good health (defined as the absence of any clinically relevant abnormalities as determined by the investigator) based on physical and neurological examinations, medical history and clinical laboratory values completed during the Screening Visit (Visit 1).
5. In the opinion of the investigator, the parent(s)/caregiver(s) is (are) willing and able to comply with the study procedures and visit schedules.

3.2.2. Exclusion Criteria

Patients will be excluded for any of the following:

1. Is considered by the investigator, for any reason (including, but not limited to, the risks described as precautions, warnings, and contraindications in the current version of the [Investigator's Brochure](#) for Cannabidiol Oral Solution) to be an unsuitable candidate to receive the study,
2. Known or suspected allergy to cannabidiol.
3. History of an allergic reaction or a known or suspected sensitivity to any substance that is contained in the investigational product formulation.
4. Use of any cannabidiol/cannabis product within 30 days of study entry.
5. Patient is diagnosed or at high risk of having tuberous sclerosis.
6. Patient has received treatment with either vigabatrin, ACTH, or high-dose steroids previously.
7. Previous or concomitant therapy with felbamate, clobazam, valproic acid, or the ketogenic diet.
8. Patient currently on any disallowed CYP3A4-related medication listed in [Appendix 1](#) (phenytoin, fluvoxamine, carbamazepine, and St. John's Wort).
9. Previously received any investigational drug or device or investigational therapy within 30 days before Screening.

10. Clinically significant abnormal laboratory values, including: liver function tests (LFTs) such as albumin, direct bilirubin, total bilirubin, aspartate aminotransferase (AST), and alanine aminotransferase (ALT) ≥ 3 times the upper limit of normal (ULN). The investigator may deem the patient eligible if he or she judges the laboratory values to be not clinically significant.

3.3. Removal of Patients from Therapy or Assessment

Patients will be allowed to discontinue their participation in the study at any time for any reason (withdrawal of consent).

The inclusion/exclusion criteria in [Sections 3.2.1](#) and [3.2.2](#) are to be followed explicitly. If a patient who does not meet enrollment criteria is inadvertently enrolled, that patient should be withdrawn from the study and the Sponsor must be contacted.

In addition, participation in this clinical study may be discontinued by the Investigator or by the sponsor for any of the following reasons:

- Intolerable side effects of the study product.
- Changes in medical status or medical condition of the patient such that the Investigator believes that patient safety will be compromised or that it would be in the best interest of the patient to stop treatment.
- Patient safety or welfare is at risk.
- Non-compliance with study visits, defined as failure to perform any portion of scheduled assessments or procedures.
- Any unforeseen event that in the opinion of the treating physician and/or the Principal Investigator, will prevent the research participant from continuing in this study.
- Sponsor decides to stop the study.

In the event of a patient's withdrawal, the investigator will promptly notify the sponsor.

Patients who withdraw from the study early will complete an Early Withdrawal Visit. Should any patient choose to withdraw early from the study, they will be advised of the safety precautions to be taken and will be followed until resolution of any AE or until the unresolved AEs are judged by the investigator to have stabilized.

If a patient discontinues the study prematurely, the investigator's impression of efficacy and tolerability of the study drug, as evaluated by the Clinical Global Impression – Global Improvement (CGI-I) assessment, will be assessed and recorded immediately before discontinuation. If possible, the parent/caregiver will be encouraged to have an Early Withdrawal visit with 9-hour video-EEG.

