8.3. Analysis Populations

Statistical analysis will be done on the following populations:

- Intent to Treat (ITT) Population: The ITT Population will include all patients who were randomized.
- Safety Population: The Safety Population will include all patients who were treated with at least one dose of the study drug. Patients will be analyzed according to the actual treatment they receive.
- PK Population: The PK Population will include all patients who were treated with at least one dose of the study drug and have at least one usable PK measurement.

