8.4.3. Efficacy Analyses

A 9-hour video EEG will be conducted during the Screening Period (Baseline) and a 24-hour video EEG will be conducted from Day 14 to Day 15 of the Initial Treatment Period. In addition, to confirm parent/caregiver report of relapse or complete resolution a 9-hour video EEG will be conducted during the Extended Treatment Period. For each video EEG, the number of spasms will be counted and the presence of hypsarrhythmia determined. Change from Baseline for each measure will be summarized by the median difference. Patients will be defined as having Complete Response, Partial Response, or Non-Response on Day 15 as defined in [Table 2](#), the percentage of patients who achieve a Complete Response and Partial Responders in each treatment arm will be compared using a chi-square test.

The results of the CGI-I assessments will be listed and summarized by descriptive statistics as appropriate. The responses to the seizure diary will also be summarized by dose level and scheduled time point. All efficacy summaries will be based on the ITT Population.

Details of these summaries will be provided in the SAP. For all inferential statistical tests, a 2-sided type I error rate of 0.05 will be used throughout.

For the secondary efficacy endpoints, to maintain the trial-wise type I error rate at 0.05, a fixed sequence multiple comparisons correction with fallback will be used. The assignment of alpha levels to hypotheses being tested will be specified in the SAP.

For endpoints that are continuous in nature number, the number of observations, mean, median, minimum and maximum, and standard deviation (SD) values will be presented as descriptive statistics. For inferential statistics:

- If the normality assumption is met, analysis of covariance (ANCOVA) using the baseline value as a covariate will be used.
- If the normality assumption is not met, a rank-ANCOVA analysis i.e., an ANCOVA analysis on rank-transformed data or other non-parametric methods will be used.
- Time to event analyses will be described with Kaplan-Meier curves and treatment groups compared with log-rank tests.

For endpoints that are categorical in nature, frequency, counts, and percentages will be presented as descriptive statistics, and a chi-square test will be used for inferential statistics.

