8.4.6. Missing Data

There will be no imputation of the missing values. Patients without a video EEG assessment on Days 14-15 will be considered non-responders for all EEG-related endpoints. Percentage of spasm-free days will be calculated based on the number of entries (up to 15 days per measurement period). A sensitivity analysis may be conducted to assess the impact of the missing values on the final analysis. The sensitivity analyses will be detailed in the SAP.

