9.8. Changes to the Protocol

The investigator may not deviate from the protocol without a formal protocol amendment established and approved by the appropriate IEC/IRB, except when necessary to eliminate immediate hazards to the patient or when the change involves only logistical or administrative aspects of the study. Any deviation may result in patient withdrawal from the study and rendering that patient not available for data evaluation.

The Investigator or sub-investigator should document any deviation from the protocol and the reason. If the Investigator performs a deviation from the protocol or a change of the protocol to eliminate an immediate hazard(s) to patients, the record should be immediately submitted to the sponsor, the Clinical Research Unit (CRU), and the IRB by the Investigator. The IRB will provide expedited review and approval. After the Investigator has obtained approval of the IRB, the Investigator should obtain written permission of the CRU and written agreement of the sponsor.

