### **7.3. General Post Text Summary Table and Individual Subject Data Listing Format Considerations**

## **8. PATIENT DISPOSITION AND PROFILE OF SCREEN FAILURES**

The number of patients in the ITT and Safety Analysis Population will be summarized along with reasons for early discontinuation from the study. A summary table of protocol deviations will also be presented. All protocol deviations along with patient's eligibility criteria will be listed for the Safety Analysis Population.

Discontinuation reasons are as follows:

- Inadvertently enrolled (enrollment criteria not met)
- Investigator decision
- Adverse Event
- Subject withdrew consent
- Lack of protocol compliance
- Subject attempted suicide or is at risk of suicide
- Sponsor decision
- Subject becomes pregnant
- Abnormal laboratory values
- Lost to follow-up
- Death
- Other

The following important (clinically) protocol deviations, as identified in the clinical trial management system (CTMS), will be summarized:

- Administrative Criteria
- Eligibility and Entry Criteria
- IP Compliance
- Informed Consent
- Laboratory Assessment Criteria
- Serious AE Criteria
- Study Procedures Criteria
- Regulatory or Ethics Approvals Criteria
- Visit Scheduled Criteria
- Other Criteria

Supportive listings will also be provided:

- Allocation to treatment
- Protocol deviations
- Subjects eligibility criteria

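### Protocol 3.3 withdraws ineligible patients from the study, which before Day 14 loses the primary outcome; Protocol 9.8 and SAP 10.8 also allow exclusions that the ITT definition does not

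*Protocol*

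**What the plan says.** - **Ineligible patients.** Protocol 3.3: "If a patient who does not meet enrollment criteria is inadvertently enrolled, that patient should be withdrawn from the study". SAP 8 lists inadvertent enrolment among the reasons for discontinuation, so the rule reaches patients already in the trial. No section keeps such a patient in follow-up.
- **EEG on early withdrawal.** Protocol 3.1: "A video EEG is not required for patients who decide to withdraw during the Initial Treatment Period". Protocol 7.2.5, which covers termination for any reason, provides the 9-hour withdrawal EEG only for patients who reached the Extended Treatment Period. Protocol 3.3 encourages one more generally, if possible.
- **Missing Day 14 to 15 EEG.** Protocol 8.4.6: "Patients without a video EEG assessment on Days 14-15 will be considered non-responders for all EEG-related endpoints". SAP 6.4.4 says instead that missing values are not imputed and that assessments use the observed data.
- **Deviations.** Protocol 9.8: "Any deviation may result in patient withdrawal from the study and rendering that patient not available for data evaluation".
- **Populations.** Protocol 8.3: "The ITT Population will include all patients who were randomized". Protocol 8.4.3: "All efficacy summaries will be based on the ITT Population". SAP 6.4.2 agrees with both. SAP 10.8 nevertheless plans a listing of patients excluded from the ITT Population, with reasons, and gives no criteria for exclusion.

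**The concern.** An eligibility error is a fact about the patient at entry. It is no reason to stop measuring the outcome once the patient has been randomised. Here the error ends study participation, so an infant whose spasms and hypsarrhythmia would have been found resolved at Day 14 to 15 is never assessed. What happens next depends on the document: a failure under the Protocol, no outcome under the SAP.

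The deviation clause in Protocol 9.8 raises a different problem. If it is used, a randomised patient leaves the primary comparison after randomisation, possibly when the clinical course is already known. Protocol 6.1 allows the investigator to read the EEG first, and Protocol 9.5.2 has the sponsor review all data before lock. No section requires decisions on eligibility or deviations to be made without knowledge of the patient's course. Exclusions made that way can bias the comparison that ITT is meant to protect.

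**Working it through.** **Step 1: one patient followed through the text.** Suppose ineligibility is found on Day 8.

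1. Protocol 3.3: withdrawn from the study.
2. Protocol 3.1 and 7.2.5: no EEG is required. A 9-hour EEG, if done, is still not the 24-hour Day 14 to 15 EEG that defines the primary endpoint in Protocol 8.1.1.
3. Protocol 8.4.6: non-responder, kept in the denominator.
4. SAP 6.4.4: no observed outcome, so not in the comparison. SAP 11.3 counts as failures those discontinued for safety or tolerability, which does not cover this patient.

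If ineligibility is found on Day 20, the EEG exists and its result stands under both documents.

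**Step 2: the plan's own figure.** Inputs from Protocol 8.2: 130 and 60 patients, 60% and 40% response, two-sided alpha 0.05, stated power 80%. With the pooled normal approximation:

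- pooled rate = (60 × 0.40 + 130 × 0.60)/190 = 0.537
- se0 = √[0.537 × 0.463 × (1/60 + 1/130)] = 0.0778
- se1 = √[0.24/60 + 0.24/130] = 0.0765
- power = Φ[(0.20 − 1.96 × 0.0778)/0.0765] = 73.3%

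Exact enumeration of the chi-square test gives 73.0%. The stated 80% is not reproduced. That gap is a separate matter and is not caused by the withdrawal rule; 73% is the starting point below.

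**Step 3: effect of the withdrawal rule.** Let w be the share of each arm withdrawn as ineligible before Day 14. The documents give no value, so w is an assumption. Affected patients are assumed to respond at the planning rates if they were assessed.

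- Non-responder route (Protocol): rates become 0.60(1 − w) and 0.40(1 − w), so the difference is 0.20(1 − w).
- Exclusion route (SAP observed data, or Protocol 9.8): rates are unchanged and arm sizes become 130(1 − w) and 60(1 − w).

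| w | Patients of 190 | Difference, non-responder route | Power, non-responder route (exact) | Same, normal approx. | Power, exclusion route (normal approx.) |
|---|---|---|---|---|---|
| 0 | 0 | 20.0 points | 73.0% | 73.3% | 73.3% |
| 3% | 5.7 | 19.4 | 70.5% | 70.5% | 72.0% |
| 5% | 9.5 | 19.0 | 68.7% | 68.7% | 71.0% |
| 10% | 19 | 18.0 | 64.3% | 64.0% | 68.7% |

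**Step 4: unequal shares.** Take a true response of 40% in both arms, with withdrawals scored as failures. The two-sided rejection rate, by normal approximation, is 5.9% if 5% are withdrawn in the CBD arm only, 5.7% if 5% are withdrawn in the placebo arm only, and 8.0% if 10% are withdrawn in the placebo arm only. These cases illustrate systematic imbalance; chance imbalance does not inflate the error rate.

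**Step 5: deviations against the ITT definition.** Protocol 8.3 and SAP 6.4.2 set one condition for ITT, randomisation. A randomised patient made unavailable for evaluation under Protocol 9.8, or excluded under SAP 10.8, meets that condition and yet is left out. Both statements cannot apply to the same patient.

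**The case against.** Several stronger readings are tempting, and the documents do not support them.

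- A reader might infer that non-responder scoring itself breaches ITT. It does not: the patient stays in the denominator of all randomised patients. The cost is a lost outcome and a diluted difference.
- A reader might infer that ineligibility automatically means treatment failure. It does so only if it is acted on before the Day 14 to 15 EEG, and only under the Protocol's rule.
- A reader might infer that Protocol 9.8 orders exclusion. It is permissive and sits in a section on changes to the protocol. Protocol 9.5.2 ties inclusion to the specified population definitions, and SAP 1 settles analysis decisions before unblinding. This helps but does not cancel the 9.8 clause, and SAP 10.8 still foresees exclusions.
- A reader might infer arm-directed bias. Protocol 4.2, 4.3 and 6.1 conceal the schedule, blind study personnel and data management, and blind the central reader. Knowledge of the arm is therefore restricted; knowledge of the patient's course is not.
- A reader might infer that eligibility errors are likely. Protocol 4.2 places randomisation after confirmation of eligibility, and 3.2.1 requires a central EEG read. Some criteria are worded inconsistently: tuberous sclerosis is excluded on suspicion in the synopsis but on high risk in 3.2.2. That shows room for error, not its frequency.

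It can also be said that the SAP was written to a protocol version of 30 October 2017, describes 180 patients, and may be revised. That may explain the missing-data conflict, but it does not resolve it.

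**Conclusion.** The point stands in three parts. Protocol 3.3 ends study participation for ineligible patients and, before Day 14, loses a primary outcome that could have been observed. The Protocol and SAP then treat that patient differently. Protocol 9.8 and SAP 10.8 allow exclusions that the ITT definition rules out.

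The size is modest. Under the Protocol's rule, power falls by 2.5, 4.3 or 8.7 percentage points for w of 3%, 5% or 10%. These figures rest on an assumed w, on every affected patient being withdrawn before Day 14, and on equal shares in the two arms. If only a few patients are affected and the blind holds, the effect on the result is small. The change is still worth making because it removes an avoidable loss of data and a route to post-randomisation exclusion.

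**What to change.** 1. **Protocol 3.3.** Separate discontinuation of study drug from withdrawal from the study. Leave the study-drug decision to the existing clinical provisions. Add, for example: a randomised patient later found ineligible remains in follow-up, has the scheduled Day 14 to 15 video EEG where the caregiver agrees, and is analysed in the ITT Population as randomised. Make 3.1 and 7.2.5 consistent with this.
2. **Protocol 9.8 and SAP 10.8.** Delete the part of the 9.8 sentence on availability for data evaluation. Reword SAP 10.8 so that no randomised patient is excluded from ITT, whatever the eligibility finding or deviation.
3. **SAP 6.4.4.** Align it with Protocol 8.4.6 on a missing Day 14 to 15 EEG, so that there is one rule for the primary endpoint.

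The cost is a few sentences in a protocol amendment and an SAP revision, which SAP 1 already provides for before database lock. Eligibility deviations are already to be summarised under SAP 8. The 24-hour EEG is already in the schedule of events, but patients who would otherwise have left will need that inpatient stay. Some ineligible or off-treatment infants will contribute data, as ITT already intends.
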